Aim 1: Prevention. We will apply new anatomical and functional LN imaging approaches to identify LN profiles specific to biopsy-confirmed metastatic LNs; findings could be used to better inform LN removal and reduce the incidence of benign LN dissection. We will incorporate healthy female controls to serve as a comparison to the patient population.

Aim 2: Progression. We will improve our understanding of secondary lymphedema risk progression following cancer therapy by testing the hypothesis that superficial tissue profiles and subcutaneous adipose accumulation are more prevalent in patients experiencing lymphedema progression, and thereby could be used to triage patients for aggressive therapies prior to overt symptoms and irreversible damage.

Aim 3: Therapy. We will perform a repeated-measures cross-over trial to test the hypothesis that mobilization of protein enriched hardened tissue using graded negative pressure therapy in conjunction with complete decongestive therapy (CDT) is more effective to standard CDT alone for secondary lymphedema management. Both of these conservative physical therapy treatments are commonly employed for treatment of secondary lymphedema and the Vanderbilt Lymphedema Clinic utilizes the graded negative pressure therapy as a component of treatment. Additionally we will perform a subgroup of 1-time only hour treatment with before and after MRI and nonMRI measurements for additional immediate treatment impact in CDT, CDT with graded negative pressure, or exercise and self management treatment strategies alone as commonly performed in outpatient physical therapy clinics and at home for the management of BCRL.

The overarching goal is to develop objective markers of lymphatic dysfunction that can be used in emerging therapeutic trials of cancer and lymphedema therapies to be used to reduce both the incidence and severity of symptoms associated with this prevalent and chronic condition.

Aim (1). To compare *in vivo* anatomical and novel molecular imaging contrasts between LNs with versus without biopsy-confirmed metastasis.

Hypothesis (1). Biochemical LN profiles quantified from noninvasive chemical exchange saturation transfer (CEST) MRI provide discriminatory potential for distinguishing metastatic versus benign LNs pre-operatively. These biochemical profiles are more discriminatory than anatomical measures of LN morphology.

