approximately 90minutes. Patients undergoing 2-year monitoring will also undergo these non-MRI measurements at baseline, and every 5-7 months (targeting at 6months) up to 5 total visits within 2 years; and for this same group an MRI will be done at Visit 1 and then as needed based on symptoms, clinical therapies provided increasing risk of lymphedema such as radiation, and non-MRI measures at subsequent follow-up visits within the 2 year time period. For these follow-up visits non-involving MRI, the visits last approximately 30 minutes.

Perometer

L-Dex

LymphaTouch

MoistureMeter D/LymphaScanner

InBODY 770 (Body Composition)

SkinFibroMeter

5. For subjects enrolled in Aim 3 of this study, they will receive the above mentioned non-MRI and MRI measures (#2) at Visits 1, 11, 12 and 22. In addition the MLD screening form will be completed on Visit 1 in preparation for this component of their CDT during subsequent treatment visits, as well as completion of the Functional Outcome Measures (PSFS and UEFI) patient self-reports will be done on Visits 1, 11, 12 and 22 to establish baseline functional level and monitor during treatments. Then they will receive their assigned therapy intervention (CDT alone or CDT with graded negative pressure) at Visits 2-10 and 13-21. For Group 1, the first course of treatment will be CDT alone, then the second course of treatment will be CDT with graded negative pressure. For Group 2, the first course of treatment will be CDT alone, then the second course of treatment will be CDT with graded negative pressure. During all courses of treatment, it will consist of 9 visits within 6-8 weeks at 75minutes duration each visit, twice per week for three weeks and then once per week for 3-5 weeks. There will be a 4-8 week washout period between Visit 11 and Visit 12.
6. For the subgroup of subjects enrolled in the 1 time hourly treatment visit of Aim 3, they will receive the above mentioned MRI and nonMRI measures before and immediately following the 1x hourly treatment. The PSFS and UEFI questionnaires will not be administered for this 1x treatment visit only. The participants will undergo (i.) CDT alone, (ii.) CDT with graded negative pressure, or (iii.) exercise and self management treatment. This subgroup participation may involve undergoing all three of the single treatment options on different study dates if the participant is interested otherwise the study only only involves this one-time study visit.

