7. Post processing of this MRI data will be overseen by [name] and performed by [name] or a member of the KSP team. The KSPs analyzing the data in Aim 3 will be blinded of the subjects' group assignments until after data processing and statistically analysis.
8. Images from cases showing examples of findings that correlate with changes in lymphatic structure and function will be de-identified before inclusion in any potential publication or presentation of the results of this pilot study and saved by [name].

9. Compensation will be as follows:
 - a. Aim 1 = \$60
 - b. Aim 2 = \$20 (non-MR measures) / \$40 (MRI)
 - c. Aim 3
 - i. Scan 1 for 1st Treatment = Choice of check for \$60 OR 1 Velcro day and night-time compression wrap for arm and hand
 - ii. If all 9 treatments + exit visit MRI/non-MRI measures complete = \$60
 - iii. After 4-8 month washout period
 - iv. Scan 1 for 2nd Treatment = \$60
 - v. If all 9 treatments + secondary MRI complete = \$60
 - vi. If completes all parts of the study, will earn additional \$50
 - vii. Total = \$120+\$120+\$50 = \$290 OR Total = 1 Velcro compression garment (free) + \$60 + 120 + \$50 = \$230 + 1 Velcro compression garment
 - d. Subgroup Aim 3 each one-time visit treatment (pre and post MRI and non MRI measures = \$80

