9.0 Privacy/confidentiality issues

The data files generated by the MRI scanner, Perometer and L-Dex software are coded using a project name and unique number generated sequentially. Only the investigators will have the key to the subject codes. Image analysis will use the coded files. The safety surveys described above include questions about sensitive health issues. This information will remain with the signed consent form in a secured area near the scanner. These records will remain in the investigators' possession for ten years following the termination of the study and will then be destroyed.

Risks to participants are minimized by limiting this prospective study to subjects meeting the inclusion/exclusion criteria. Access to PHI will be limited to the PI and co-investigators. All data will be de-identified before publication and/or presentation of the results of this study. All PHI used in this study will be kept under lock and key in [name] or [name] office. The primary risk in this study involves the disclosure of protected health information. This risk is reasonable, given the above precautions, in relation to the potential benefit to both future patients and society in general by the possibility of better understanding and treating lymphedema.

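### As written, both Aim 3 cross-over groups receive the therapies in the same order, so blinding analysts to group does not conceal treatment, and no section masks visit or period

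*Combined protocol and SAP*

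**What the plan says.** All references are to the combined protocol and SAP.

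- **Masking rule (section 5.0, item 7).** This is the only masking statement for Aim 3: the staff analysing the data "will be blinded of the subjects' group assignments" until processing and statistical analysis are finished. It names group. It does not mention visit, period or treatment.
- **Treatment order (section 5.0, item 5).** "For Group 1, the first course of treatment will be CDT alone, then the second course of treatment will be CDT with graded" negative pressure. The next sentence reads: "For Group 2, the first course of treatment will be CDT alone, then the second course of treatment will be CDT with graded" negative pressure. Apart from the group number, the two sentences are identical.
- **Measurement visits (section 5.0, item 5).** Participants have "non-MRI and MRI measures (#2) at Visits 1, 11, 12 and 22". Visits 1 and 11 bracket the first course, and Visits 12 and 22 bracket the second.
- **Declared design (section 2.0, Aim 3).** "We will perform a repeated-measures cross-over trial to test the hypothesis". The analysis in section 8.0 compares pre-to-post change between the two therapies and plans a carryover test and a treatment-by-period term.
- **File coding (section 9.0).** MRI, Perometer and L-Dex files are "coded using a project name and unique number generated sequentially". Image analysis uses the coded files, and the investigators hold the key to the subject codes. The section does not say whether the number runs per subject or per scan, or whether the people who process images also hold the key.

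**The concern.** Blinding to group conceals treatment only if the groups differ in the treatment given at a given time. With one common order, group carries no information about treatment and period carries all of it. The mask that item 7 promises can be kept perfectly and still leave the treatment known to an image reader or analyst who knows the course.

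The stake lies in the imaging half of the primary objective. Section 8.0 names imaging metrics of lymphatic clearance or the PSFS score. PSFS is a patient self-report and no masking of participants is described, so imaging is the part that masked reading can protect. The power statement is one-sided in the direction that favours negative pressure. A reading drift in that direction would therefore add directly to false positives.

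**Working it through.** **1. What group masking conceals.** Let q be the share of participants on one order and 1 − q the share on the reverse order. Someone who knows the course but not the group names the treatment correctly, by best guess, with probability max(q, 1 − q).

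- Text as written, one common order: q = 1, so the probability is 1.0.
- Opposite orders at 1:1 (assumed, since no allocation ratio is given): max(0.5, 0.5) = 0.50, no better than chance.
- Opposite orders at 2:1 (assumed): max(2/3, 1/3) = 0.67.

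Group masking therefore works if the orders differ and does nothing for treatment if they are the same.

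**2. Who knows the course.** The planned test in section 8.0 forms a change within each course for each participant and compares the two courses. The statistical step must therefore arrange data by course. Under a common order, whoever does this knows the treatment unless the courses carry neutral labels. This route does not depend on file numbers. For image reading, no section describes random scan codes, removal of acquisition dates or a shuffled reading order, so visit and period are not stated to be masked there either.

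**3. What remains if the orders differ.** A reader who sees pre versus post but not treatment might favour improvement by an amount b in each course. With true changes D1 (CDT alone) and D2 (with negative pressure), the contrast becomes (D2 + b) − (D1 + b) = D2 − D1. The bias cancels to the extent that b is the same in both courses.

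**4. Illustration of size.** The plan gives no figure to reproduce. Assumptions:

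- the same-order text is literal and the reader knows the course;
- there is no true treatment difference;
- the test is a paired t-test at one-sided 5%;
- reading shifts the within-person difference by d standard deviations towards negative pressure;
- n is assumed, because the documents state no sample size.

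The rejection probability is P(T > c), where T is noncentral t with n − 1 degrees of freedom and noncentrality d√n, and c is the 95th percentile of central t. For n = 20 and d = 0.2, c = 1.729, the noncentrality is 0.2 × √20 = 0.894, and the probability is 0.217.

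| n (assumed) | c | d = 0.1 | d = 0.2 | d = 0.3 |
|---|---|---|---|---|
| 10 | 1.833 | 8.8% | 14.5% | 22.2% |
| 20 | 1.729 | 11.2% | 21.7% | 36.3% |
| 40 | 1.685 | 15.3% | 34.4% | 58.7% |

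Without a shift, every entry would be 5%.

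**The case against.** **The order may be a copying error.** The Group 2 sentence repeats the Group 1 sentence, and it conflicts with the cross-over label, the randomization heading of section 4.0 and the carryover and period terms in section 8.0. If the orders differ, group masking does its job, the table above does not apply, and what is left is the pre/post visibility of step 3. This stands, and it is why reconciling item 5 comes first in the fix. It does not remove the point, because the current text is the only statement of the order.

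**The file numbers may reveal nothing.** A reader might infer from section 9.0 that a later number means a later visit. The documents do not establish this. The reference to a key for subject codes fits one number per subject, which would show no visit. Even per-scan numbers rank visits only if one participant's files can be linked. Sequential numbering is a possible route to the visit and no more.

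**The stated blinding can still be kept.** It would be tempting to say that the promised blinding fails. The promise concerns group assignment, and nothing shows that it would be broken. What fails, on the text as written, is concealment of treatment.

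**The one-time subgroup.** A reader might extend the argument to it. It has three possible treatments and no fixed order, so knowing pre from post does not reveal which was given. Group assignment in item 7 could also be read to cover the assigned treatment there.

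**The size is hypothetical.** This is right. Both n and d are assumed. The documents do not describe how the lymphangiography score is obtained, so its dependence on the reader is plausible but not documented.

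**Conclusion.** The point holds in a limited form. Item 7 masks group only, and item 5 gives both groups the same order, so as written the masking conceals nothing about treatment from anyone who knows the course. No section masks visit or period during image processing.

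The weight of the point depends on what item 5 was meant to say. If the order is literal, course identifies treatment with certainty, and the false-positive rates in the table show what a reading shift could do. If the orders were meant to differ, the remaining concern is small. In neither case do the documents show that bias will occur. The change is worth making because it is cheap and protects the image measurements under both readings.

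**What to change.** 1. **Section 5.0, item 5.** Reconcile the Group 2 sentence with the cross-over design declared in section 2.0 and the analysis in section 8.0, so that the document states one consistent set of sequences.
2. **Section 5.0, item 7.** Add that, before image processing, each Aim 3 scan receives a random per-scan code, acquisition dates are stripped, and scans are read in random order. Applying this to the one-time subgroup as well keeps a single procedure.
3. **Key.** State that a current team member who does not read scans holds the key until image measurements are locked.
4. **Analysis.** Keep treatment and group labels masked through statistical analysis, so that the period for which item 7 already promises masking is not shortened. The key holder can supply the paired measurements with courses under neutral labels.
5. **Section 9.0.** Say whether file numbers run per subject or per scan, and whether image readers have access to the subject key.

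The cost is a renaming script and a code list, with no extra scans, visits or readers. The downside is that scans are read in batches and not as they arrive.

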8.0 Statistical analysis plan

Statistical analysis will be overseen by statistician co-investigators. Means, standard deviations, and ranges for continuous variables will be recorded, along with tests for normality and homoscedasticity. The primary statistical objective is to assess whether the changes, pre- vs. post-intervention, in internal imaging metrics of lymphatic clearance or PSFS score are different for the standard CDT therapy or CDT therapy with negative pressure. First, a Student's t-test or Wilcoxon signed-rank test (depending on normality results) will be applied to test the difference between each measurement for the same subject for each of the two therapy sessions. We will also test the difference of any potential carryover effect and we will apply a general linear model approach, in which we include the treatment and treatment-period interaction in the model. Power calculations are based on our preliminary data that observed an improvement in PSFS in five patients on CDT with negative pressure vs. CDT alone, as well as an ability to detect a mean change in T_2 and lymphangiography score pre- vs. post-MLD of N. With the premise that CDT with negative pressure will be at least as good as CDT without negative pressure, with the proposed sample size, we will have 80% power to detect a 40% reduction rate with one-sided type I error = 5%.

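### The optional compression wrap paid at the first Aim 3 baseline scan is an unrecorded co-intervention that can bias the treatment comparison if both groups follow the order as written

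*Combined protocol and SAP*

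**What the plan says.** **Payment.** Section 5.0, item 9 sets the Aim 3 compensation. The first entry reads "Scan 1 for 1st Treatment = Choice of check for" $60 or "1 Velcro day and night-time compression wrap for arm and hand". The corresponding entry for the second course, "Scan 1 for 2nd Treatment", is $60 with no alternative. The totals agree: $120 + $120 + $50 = $290 in cash, or one garment plus $60 + $120 + $50 = $230. The wrap therefore replaces the first payment only.

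**Measurement.** Section 5.0, item 5 schedules the "non-MRI and MRI measures (#2) at Visits 1, 11, 12 and 22". The first course runs from the Visit 1 baseline to the Visit 11 outcome, and the second from Visit 12 to Visit 22.

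**Order.** The same item states: "For Group 1, the first course of treatment will be CDT alone, then the second course of treatment will be CDT with graded negative pressure". Its sentence on the other group begins: "For Group 2, the first course of treatment will be CDT alone", again followed by CDT with negative pressure. The two groups have the same order, although section 2.0 describes a cross-over.

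**Analysis.** Section 8.0 compares pre-to-post changes in imaging metrics or PSFS between the two therapies. It uses a paired test first, then a general linear model "in which we include the treatment and treatment-period interaction in the model". It names neither a period main effect nor a term for compression use.

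The plan does not say when the wrap is handed over, whether it is to be worn, or whether its use is recorded.

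**The concern.** An arm-and-hand compression wrap can plausibly act on what Aim 3 measures in people with arm lymphedema: arm volume, extracellular fluid and tissue fluid on MRI. Tied to the first scan and to no later one, it would reach some participants, by their own choice, after the first baseline and before the first outcome. They would still have it during washout, at the Visit 12 baseline and through the second course.

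The primary contrast is a within-person difference between two changes. A co-intervention that starts inside one of those changes and not the other goes straight into the contrast. In the order as written, the first change is always the CDT-alone change, so a benefit from the wrap would be credited to CDT alone and would count against the trial's own hypothesis. Because uptake is neither recorded nor modelled, the analysis could not show that this had happened.

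**Working it through.** **1. The plan's own figure.** Section 8.0 claims 80% power for a 40% reduction rate at one-sided 5%. This cannot be reproduced: no sample size, standard deviation or base rate is given, and the 40% is not tied to one endpoint. Sample size, uptake and wrap effect below are therefore assumptions.

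**2. Notation.** Let D be a participant's improvement under CDT with negative pressure minus improvement under CDT alone, in units of its SD. Let p be the share choosing the wrap, and w the gain it adds to the first-course change.

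**3. Order as written (CDT alone first in both groups).** The wrap adds w to the CDT-alone change of those who take it, so bias in D = −p × w.

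| p | w | Bias (SD) |
|---|---|---|
| 0.25 | 0.2 | −0.05 |
| 0.5 | 0.2 | −0.10 |
| 0.5 | 0.5 | −0.25 |
| 0.75 | 0.5 | −0.375 |

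**4. Effect on power.** For a paired one-sided 5% t-test (noncentral t) with n = 20, 80% power corresponds to a true difference of 0.577 SD.
- Shift of 0.10: 0.577 − 0.10 = 0.477, power 66%.
- Shift of 0.25: 0.577 − 0.25 = 0.327, power 41%.

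These treat the shift as the same for everyone. Since only some take the wrap, the SD of D also rises by a factor √(1 + p(1−p)w²) = √(1 + 0.25 × 0.25) = 1.03 in the second case, and power is then about 39%. The sample size matters: setting the true difference to give 80% each time, a 0.25 SD shift leaves about 55% at n = 10 and 24% at n = 40.

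**5. Opposite orders (1:1).** The wrap now adds to CDT alone in one group and to CDT with negative pressure in the other. With p₁ and p₂ the uptake in the CDT-alone-first and negative-pressure-first groups, bias = w × (p₂ − p₁)/2.
- Equal uptake: bias 0.
- Uptake differing by 20 points: 0.2 × 0.20/2 = 0.02 SD to 0.5 × 0.20/2 = 0.05 SD.

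With n = 20, p = 0.5 and w = 0.5, simulation gives mean bias about 0, with power 76% for the plain paired test and 78% with period in the model. A normal approximation agrees, using 1.645 + 0.842 = 2.487:
- Plain paired test: SD √(1 + 0.0625 + 0.0625) = 1.061, and 2.487/1.061 − 1.645 = 0.70, power 76%.
- Period-adjusted: SD √1.0625 = 1.031, and 2.487/1.031 − 1.645 = 0.77, power 78%.

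**6. What a period term can do.** It removes the average wrap effect only if the orders differ. If both groups have the same order, period and treatment cannot be separated.

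**The case against.** The strongest reply is that the large figure depends on a different defect. The Group 2 sentence repeats the Group 1 order, yet a cross-over, two numbered groups, blinding to group assignment and a treatment-period interaction make sense only if the orders differ. A copying error is likely. With opposite orders the expected bias vanishes and little power is lost. If the orders really are identical, every time trend is confounded with treatment, with or without the wrap. This stands, and it makes the bias conditional. It does not remove the issue: correcting the sequence alone leaves a self-chosen, unrecorded device in the first course.

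Second, the mechanism is partly inferred. The document ties a payment to a scan; it does not say that the wrap is given that day or worn. It does not define the compression content of CDT or describe garments already in use. If most participants already use compression, the wrap may add little. Nothing in the document gives its effect on the imaging metrics or PSFS that section 8.0 names. This also stands.

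Two stronger readings are tempting. A reader might infer that the washout cannot restore baseline, or that less room for improvement remains in the second course. The document supports neither as fact: each course has its own baseline, a carryover test is planned, and no ceiling or floor is shown. A reader might also infer that compression should be held back until the last visit. That is a matter of care, and the statistical point does not need it.

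**Conclusion.** The concern holds conditionally. An optional device that can plausibly act on the outcomes is offered at the first baseline scan only, and the plan neither standardises, records nor adjusts for it. If it is handed over then and worn, the sequences as written place its whole first-course effect in the CDT-alone change, and the comparison can be biased against CDT with negative pressure. The illustrated fall from 80% to about 41% power rests on n = 20, 50% uptake and a 0.5 SD effect, none of which is in the document.

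It would be wrong to conclude that the comparison is biased whatever the order, or that 41% is the trial's expected power. With opposite orders, the same assumptions give expected bias of about 0 and power of 76–78%. What remains is some added variance, possible persistence to the Visit 12 baseline in those who took the wrap, and about 0.02–0.05 SD of bias if uptake differs by 20 points between sequences. The change is worth making because it is cheap, not because a large bias has been shown.

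**What to change.** 1. Make the study payment for the first baseline scan the same for every Aim 3 participant, and not a device that can act on the outcomes. Any compression used in care, and its timing, stays with the treating team.
2. Record compression use at Visits 1, 11, 12 and 22, which already exist as measurement visits.
3. Name a period main effect in the section 8.0 model, and report a sensitivity analysis by wrap choice, including participants already enrolled. Because the choice is self-selected, treat that analysis as a check on robustness. The period term helps only once the orders are confirmed to differ.
4. Reconcile the Group 1 and Group 2 sequences in section 5.0, item 5 with the cross-over in section 2.0. Reconcile the washout length too: 4–8 weeks in item 5, 4–8 months in item 9.

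The cost is an amendment to the compensation and consent wording, a small amount of extra data recording, and the loss of the non-cash payment option at Visit 1.
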